### **3.6.3 Safety Variables**

- Hematology, serum chemistry and urinalysis at Visits 1, 3, 4, 5, 6, 7 and 8 (Screening, Baseline, M1, M3, M6, M9 and M12) or Early Termination (only if the subject is early terminated after Visit 3) or Final Follow-up Visit. See Section Appendix 1 for a complete list of laboratory tests to be done.
- ECG evaluation at Visits 1, 3, 6 and 8 (Screening, Baseline, M6 and M12) or Early Termination (only if the subject is early terminated after Visit 3) or Final Follow-up Up Visit
- Complete physical examination at Visits 1, 3, 5, 6, 7 and 8 (Screening, Baseline, M3, M6, M9 and M12) or Early Termination (only if the subject is early terminated after Visit 3) or Final Follow-up Up Visit
- Vital signs (sitting blood pressure, pulse, breathing, and temperature) and weight will be measured at all visits.
- Data regarding AEs and concomitant medications collected at all visits after randomization

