#### 4.2.3 Visit 3 (Week 0)

Visit 3 will occur within 5 weeks after Visit 2. During this visit, the following assessments/procedures should be performed:

- The following questionnaires/procedures will be completed: WOMAC (see Appendix 3), VAS (see Appendix 4), Lysholm scale (see Appendix 5), KOOS (see Appendix 6), IKDC (see Appendix 7), and RAND-36 (see Appendix 8).
- Measure vital signs (sitting blood pressure, pulse, breathing, and temperature) and weight.
- Record any adverse event and any change in concomitant medications.

- Perform a complete physical examination.
- Measure 12-lead ECG.
- Collect blood and urine samples for hematology, serum chemistry, and urinalysis.
- Inject the final drug product into the cavity of knee joint (Please follow the intra-articular injection instruction separately provided by the sponsor).
- Dispense a concomitant medication note.

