7.1 ADVERSE EVENTS

AEs will be coded by SOC and PT using the MedDRA (Version 18.1). The verbatim term will be included in the AE listing.

A treatment-emergent adverse event (TEAE) is defined as an AE that occur or worsen on or after the injection of study drug and before the end of the study. Only TEAEs will be included in summary tables. All AEs, treatment emergent or otherwise, will be presented in subject data listings.

The TEAEs will be summarized as the number (percentage) of subjects with TEAEs within SOC and PT. Subjects who report the same PT on multiple occasions will be counted once for the PT: under the highest severity (severe > moderate > mild) when summarized by severity and under the closest relationship to study drug when summarized by relationship. If a subject reports multiple PT for a SOC, the subject will be counted only once for that SOC.

TEAEs will be summarized as below.

- An overview table, including number of subjects with
 - TEAEs
 - serious AEs (SAEs)
 - study drug related TEAEs
 - TEAEs by severity
 - TEAEs leading to study discontinuation
 - TEAEs leading to death
- TEAE by SOC and PT
- TEAE by SOC, PT, and Severity
- Study drug related TEAEs by SOC, PT
- SAEs by SOC and PT
- TEAEs leading to study discontinuation by SOC and PT

All AE tables will be sorted by SOC and PT in decreasing frequency of the number and percentage of subjects summarized by treatment group and total.

Missing date will be imputed followed table describes how missing date information will be handled:

| Partial Missing Start or Stop Date | Imputed Start Date | Imputed Stop Date |
|--|--|-----------------------------------|
| Missing month and day, and the year is present | January 1 of that year or first dose date if the year is the same as the year of first dose date | December 31 of that year |
| Missing day, but year and month are present | First day of that month or first dose date if the year and month are the same as the year and month of first dose date | Last day of that month |
| Missing month, but year and day are present | Missing month imputed as January | Missing month imputed as December |

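### SAP 7.1 can move a partial AE start date to the injection date even when the recorded stop date is earlier

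*SAP*

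**What the plan says.** The table in SAP 7.1 has three rows for partial start dates.

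- Month and day missing: "January 1 of that year or first dose date if the year is the same as the year of first dose date".
- Day missing: "First day of that month or first dose date if the year and month are the same" as those of the first dose.
- Month missing, day present: "Missing month imputed as January". This row does not use the dose date and is not part of this point.

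No row, and no other text in the SAP, makes the imputed start depend on the recorded stop date or requires the start to be no later than the stop.

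The same section says that a TEAE "is defined as an AE that occur or worsen on or after the injection of study drug and before the end of the study". It then says "Only TEAEs will be included in summary tables", while "All AEs, treatment emergent or otherwise, will be presented in subject data listings".

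On when AEs are captured, Protocol 3.6.3 has "Data regarding AEs and concomitant medications collected at all visits after randomization". Randomization is at Visit 2, the day of liposuction, and "Visit 3 will occur within 5 weeks after Visit 2" (Protocol 4.2.3). The procedures for Visit 3, the injection visit, include recording AEs. The SAP's Safety population likewise starts from completion of Visit 2 (SAP 2.2.3).

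**The concern.** Moving a partial start to the first dose date is a cautious convention when it is unknown whether the event began before or after dosing. A recorded stop before injection answers that question. In that case the two rows override known data and produce an impossible pair of dates.

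What is at stake is the content of the AE summary tables. A short event after liposuction that had resolved before injection could be tabulated as following the injection. None of the AE summaries listed in SAP 7.1 needs a start date except to decide whether an event is treatment-emergent, so that decision is the evident use of the imputed date. The randomization code is opened subject by subject after Month 6, so a rule fixed in advance is better than a correction made during programming.

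**Working it through.** The plan states no figure that depends on this rule, so there is nothing to reproduce. The check applies the rows literally.

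**Inputs.** The two start-date rows (SAP 7.1); up to 5 weeks from Visit 2 to injection (Protocol 4.2.3); planned arms of 20 and 10 (Protocol 6.2, SAP 1.3.3). The injection date of 20 September 2017 is illustrative and not in the documents.

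**Rule.** Let D be the first dose date, E the recorded stop and S the imputed start.

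- Day missing: S = D if month and year match D; otherwise the first of the month.
- Month and day missing: S = D if the year matches D; otherwise 1 January.
- Classification, a step that the SAP does not spell out: TEAE if S ≥ D.

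Whenever the known parts match, S = D. So any stop with E < D gives S > E.

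| Case | Recorded start | Recorded stop | Imputed start | Start minus stop | TEAE by imputed start |
|---|---|---|---|---|---|
| a | Sep 2017 | 12 Sep 2017 | 20 Sep 2017 | 20 − 12 = +8 days | yes |
| b | 2017 | 25 Aug 2017 | 20 Sep 2017 | 6 + 20 = +26 days | yes |
| c | Aug 2017 | 25 Aug 2017 | 1 Aug 2017 | 1 − 25 = −24 days | no |
| d | Sep 2017 | 25 Sep 2017 | 20 Sep 2017 | 20 − 25 = −5 days | yes |

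Cases a and b show the fault. Case c shows that it needs a match with the dosing month (or year). Case d is the convention working as intended.

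**How often a qualifying event would be caught.** This rests on assumptions outside the documents: true start uniform over the 35 days before injection, injection date uniform over a year, stop date complete and before injection. Among such events with the day missing, 42.1%, 38.8%, 32.5% and 21.4% become TEAEs for durations of 1, 3, 7 and 14 days. With month and day missing, the share is 93.3% to 95.1%. These shares are conditional on a pre-injection event being recorded with a partial start. They do not say how many such events there will be.

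**Weight of one case.** 1/20 = 5 percentage points in the JointStem arm and 1/10 = 10 points in control, and only in a row where that subject is not already counted.

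**The case against.** The strongest reply is that the TEAE definition already excludes these events. Something that ended on 12 September neither occurred nor worsened on or after 20 September, and no sentence says that the imputed start overrides a recorded stop. A careful programmer could rely on that. This stands in part: misclassification follows only if status is derived from the imputed start. The impossible date pair follows either way, and the SAP does not say which reading governs.

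A reader might infer that pre-injection AEs of this kind are to be expected. The documents show only that they can be recorded. Protocol 3.6.3 and the Visit 3 procedures point that way, and the SAP provides for AEs that are not treatment-emergent. But Protocol 7.2 asks for events reported once dosing has taken place, and both schedules of assessments first mark AE assessment at Visit 3. The fault also needs a partial start, a stop known to precede injection and a matching month or year, all surviving eCRF monitoring. A start known only by year, for an event inside a five-week window, is unlikely.

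A reader might also infer that a few cases could create or reverse a difference between arms. The documents do not support this. Both arms have liposuction, no case count exists, and no safety tests are planned. The 5 and 10 points are the weight of any one subject in any row, not a property of this rule. Any error adds TEAEs rather than hiding them, and every AE remains visible in the listings.

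**Conclusion.** The point holds as a small defect in a stated rule. The two rows give a start after the stop whenever the known parts match dosing and the recorded stop precedes injection. If TEAE status is then taken from the imputed start, the event enters the summary tables contrary to the SAP's own definition.

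The size is at most 5 or 10 points per misclassified subject in an affected row, assuming the planned 20 and 10 subjects. The number of cases is unknown and probably small, and there is no reason to expect an imbalance between arms. No hypothesis test is affected. Severity is the lowest.

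**What to change.** In both rows, use the first dose date only if the stop date is missing or falls on or after the first dose date. Otherwise:

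- impute a start that agrees with the known parts and is no later than the recorded stop. Two workable choices are the stop date itself, or the later of the earliest possible date and Visit 2, capped at the stop;
- class the event as not treatment-emergent.

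The earliest possible date alone is not a good choice for the year-only row. In case b it gives 1 January, long before AE collection began. With Visit 2 a full 35 days before injection, on 16 August, the second choice gives 16 August, and the first gives 25 August. In case a the choices give 1 September or 12 September. Neither case is then a TEAE, and case d is unchanged.

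A partial stop whose latest possible date precedes injection should be treated in the same way.

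The cost is one clause in two table rows and one program condition. Protocol 7.2 already requires stop dates, so no new data are needed. The same revision should reconcile the start of AE capture (Protocol 3.6.3 against 7.2), and SAP 2.4, which plans no imputation for safety variables, with the date table in SAP 7.1.

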## **7.2 Reporting Procedures for All Adverse Events**

The investigator is responsible for ensuring that all adverse events (as defined in Section 7.1) observed by the investigator or reported by subjects after the first dose of each subject are properly captured in the subject’s medical records and reported on the eCRF.

Documentation must be supported by an entry in the subject’s file. A laboratory test abnormality considered clinically relevant, e.g., causing the subject to withdraw from the study, requiring treatment or causing apparent clinical manifestations, or judged relevant by the investigator, should be reported as an adverse event. Each event should be described in detail along with start and stop dates, severity, relationship to investigational product, action taken, and outcome

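### A start date with only the month missing is always set to January, so most such post-injection AEs from the dosing year leave the TEAE summary tables

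*SAP*

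**What the plan says.** SAP section 7.1 (Adverse Events) sets out how partial AE start dates are completed:

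- Month and day missing: "January 1 of that year or first dose date if the year is the same as the year of first dose date".
- Day missing: "First day of that month or first dose date if the year and month are the same" as those of the first dose.
- Month missing, day and year known: "Missing month imputed as January". There is no condition on the first dose date.

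The same section defines a TEAE as "an AE that occur or worsen on or after the injection of study drug and before the end of the study" and states "Only TEAEs will be included in summary tables". It also states "All AEs, treatment emergent or otherwise, will be presented in subject data listings", and section 7.1.1 adds separate listings of serious AEs, AEs leading to discontinuation, and deaths.

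The protocol is not uniform on when AE capture begins. Section 7.2 refers to events observed or "reported by subjects after the first dose of each subject are properly captured", while section 3.6.3 has "Data regarding AEs and concomitant medications collected at all visits after randomization", which would start at Visit 2 (Week -5).

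**The concern.** The first two rules prevent an incomplete date from moving an event to before the injection when the known parts agree with the dosing date. The third rule lacks that protection. The result is also illogical: a record with neither month nor day is kept as treatment-emergent, while a record that has the day can be lost.

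Safety is part of the study's primary objective (SAP 1.1.1), no safety tests are planned (SAP 7) and there is no DSMB (SAP 8.2). The descriptive TEAE tables, including those for serious and drug-related events, are therefore the main safety summary. A rule that can remove true post-injection events from them deserves correction even if it is seldom triggered.

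**Working it through.** The plan states no figure on this point, so there is none to reproduce. The check applies the three rules literally.

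**Rules.** Let D be the injection date and E the true onset, with E on or after D.

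- Month and day missing: start = D if year(E) = year(D); otherwise 1 January of year(E).
- Day missing: start = D if month and year of E equal those of D; otherwise the first of the month of E.
- Month missing: start = day(E) January, year(E).
- The event is a TEAE if start ≥ D.

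**Worked dates (illustrative).** Injection 15 June 2017, true onset 20 September 2017:

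| Missing part | Imputed start | TEAE? |
|---|---|---|
| Month and day | 15 June 2017 | yes |
| Day | 1 September 2017 | yes |
| Month | 20 January 2017 | no |

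The last date is 11 + 28 + 31 + 30 + 31 + 15 = 146 days before the injection.

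**When it happens.**

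- Injection on or after 1 February, event in the same year: the latest date the rule can give is 31 January, which is before D. Misclassification is 100%.
- Injection in January, event in the same year: the event is misclassified only if the recorded day is earlier than the injection day. With injection on 10 January, onset on 5 March becomes 5 January (lost) and onset on 20 March becomes 20 January (kept). Over all January injections with a 183-day onset window, the share is about 49%.
- Event in the following calendar year: the January date falls in that later year, after the injection. No misclassification.

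**Overall share.** The documents give no distribution of injection or onset dates. Assume injection uniform over a 365-day year and onset uniform over days 0 to W after injection, with W = 91, 183 or 365. The last two correspond roughly to follow-up to Month 6 (both arms) and Month 12 (JointStem only). The number of date pairs is 365 × (W + 1). Overall share = (share of events in the dosing year) × (share of those misclassified).

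| W (days) | Pairs | In dosing year | Misclassified, of dosing-year events | Misclassified, of all |
|---|---|---|---|---|
| 91 | 33,580 | 87.5% | 95.0% | 83.2% |
| 183 | 67,160 | 74.9% | 94.2% | 70.6% |
| 365 | 133,590 | 50.0% | 91.4% | 45.7% |

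The other two rules misclassify 0% in every scenario. Giving the month-missing rule the same first-dose floor also brings it to 0%.

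**Plausibility of the imputed dates.** Protocol section 4.1 puts screening about 7 weeks before baseline. Since 31 January plus 49 days is 21 March, for injections after about that date every January date in the dosing year precedes screening, when no study AE could have been recorded.

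**Effect of one lost subject.** 1/20 = 5 percentage points in the JointStem arm and 1/10 = 10 points in the control arm, using the planned sizes in protocol 6.2 and SAP 1.3.3.

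**The case against.** Several points limit the finding.

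- **The record type is unusual.** Day and year known with the month unknown should seldom occur. The protocol requires start and stop dates (7.2), AEs are assessed at scheduled visits, the eCRF is monitored for completeness (4.3), and each subject's data are confirmed before lock (4.2.6). This stands as to frequency, on which the documents give no figure. It does not repair the rule, and the SAP gave the case its own row.
- **The exclusion depends on the imputed date driving the TEAE flag.** The SAP does not say that an imputed date overrides other evidence of timing. That is a fair remark. However, it is the usual reading, the SAP offers no other way to set the flag, and the first-dose fallback in the other two rows has little purpose otherwise.
- **A post-injection worsening could still qualify** under the TEAE definition if it is recorded separately. This stands.

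Three stronger readings are tempting and not supported:

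- A reader might infer that the events vanish from the report. They leave the summary tables but remain in the subject listings, and serious AEs, AEs leading to discontinuation and deaths have listings of their own.
- A reader might infer that the rule favours JointStem over control. It applies to both arms and can only lower absolute rates in each. Nothing in the documents fixes the direction of any change in the between-arm contrast, and no safety test is planned that it could alter.
- A reader might treat every lost event as 5 or 10 percentage points. The tables count subjects, so this holds only if the subject has no other qualifying event in the same row.

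A simple pairing of dose days 1-365 with January days 1-28 gives 9,814 of 10,220, or 96.0%. That count ignores when the AE began and says nothing about events in the next calendar year, so the ranges from the enumeration are preferable.

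**Conclusion.** The point holds as a defect in a stated rule, limited to month-missing start dates in the calendar year of the injection and to the TEAE summary tables. For injections from 1 February on, the misclassification is certain under a literal application. Under the uniform-date assumptions it affects 91-95% of dosing-year records of this type and 46-83% of all post-injection records of this type. These are shares of a record type whose frequency is unknown and probably low, so the expected number of lost events is small.

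The bias in reported absolute AE rates runs one way, downward. If AE capture starts only after the first dose, as protocol 7.2 suggests, every recorded AE is post-injection, and the exclusions this rule causes can only be of true TEAEs. The correction is worth making because the arms are small, the safety summary is purely descriptive and the change costs almost nothing. The efficacy analyses are not affected.

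**What to change.** Add to the month-missing row in SAP 7.1: if the year is the year of first dose and the January-imputed start date is before the first dose date, impute the first dose date, unless the stop date shows that the event ended before the injection.

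The stop-date exception matters if AEs are collected from randomization, as protocol 3.6.3 says, because events between liposuction and injection could then be recorded. Rows one and two have no such exception, and it would be sensible to add it there too. The remaining cost is that a pre-injection event still ongoing at the injection, with its month missing, could be counted as treatment-emergent; the first-row rule already accepts the same error. An alternative that keeps the recorded day is to impute the earliest month that places the date on or after the injection. Either choice restores the correct classification of post-injection events.

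The cost is one sentence in the SAP and one line of code. No data collection changes.

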7.1.1 Deaths, Serious and Other Significant Adverse Events

The listings of serious AEs, AE leading to study discontinuation, and subjects who died during the study will be provided.

7.2 CLINICAL LABORATORY PARAMETERS

Laboratory assessments (hematology, blood chemistry and urinalysis) are collected at Visits 1, 3, 4, 5, 6, 7 and 8 (Screening, Baseline, M1, M3, M6, M9 and M12) or Early Termination (only if the subject is early terminated after Visit 3) or Final Follow-up Visit:

- Chemistry: Total Bilirubin, Alkaline Phosphatase, Aspartate Aminotransferase (AST) (SGPT), Alanine Aminotransferase (ALT) (SGOT), Blood Urea Nitrogen (BUN), Creatinine, Glucose, Albumin, Total protein, Sodium, Potassium, Chloride, Bicarbonate, Calcium, HCG, HIV.
- Hematology: Hemoglobin, Hematocrit, RBC, WBC, MCV, MCH, MCHC, Neutrophils (absolute), Lymphocytes (absolute), Monocytes (absolute), Eosinophils (absolute), Basophils (absolute), Platelets, PT-INR.
- Urinalysis: Specific gravity, Color, Appearance, pH, Protein, Glucose, Ketones, Bilirubin, Blood, Leukocyte esterase, WBC, RBC, Epithelial cell, Bacteria, Hyaline casts.

All laboratory parameters will be presented in Système International (SI) units. Quantitative results (including actual value and change from baseline) will be summarized using descriptive statistics by baseline and post-baseline visit for each laboratory test group above. Laboratory test results were evaluated as normal, abnormal (not clinically significant) or abnormal (clinically significant). The number and percentage of subjects of each category will be summarized by time point, treatment and total for each parameter.

All laboratory data will be included in the listings. A pregnancy listing will be provided separately.

7.3 VITAL SIGNS, PHYSICAL EXAMINATIONS FINDINGS, ECG

7.3.1 Vital Signs

Vital signs include sitting blood pressure (BP), pulse, temperature, breathing rate and weight. All vital signs will be presented in Système International (SI) units. Quantitative results (including actual value and change from baseline to each post-baseline visit) will be summarized using descriptive statistics by time point, treatment and total for each parameter.

Listings of vital signs with abnormal flags will be provided.

7.3.2 Physical Examinations

Physical examination data will be summarized separately using descriptive statistics by time point, treatment and total, for each component. Listings for physical will be provided.

7.3.3 ECG

The 12-lead ECG parameters including value and changes from baseline will be summarized using descriptive statistics by time point, treatment and total.

Subject listing will be provided. SI units will be used for both summarization and data listings. The critically significant abnormalities will also be flagged in data listings.

